5.4.2.4 Laboratory Procedures

Serum will be processed to investigate any immune responses to the ATIMP:

- 1. anti-AAV5 neutralising antibodies
- 2. anti-AAV5 antibodies by ELISA
- 3. anti-human RPGR antibodies by ELISA

Serum, saliva and lacrimal fluid will be processed to assess dissemination of ATIMP after delivery, where the number of rAAV vector genome copies will be measured using a polymerase chain reaction (PCR) approach.

Whole blood will be processed at the ______, or a CLIA-accredited molecular diagnostic laboratory in the US, for *RPGR* mutation screening. Haematology and biochemistry samples and screen will be carried out at the ______, or an accredited laboratory in the US (Table 2 Haematology and Biochemistry).

Table 2: Haematology and Biochemistry

Haematology	Biochemistry
Haemoglobin	Sodium
Haematocrit	Potassium
Erythrocytes	Chloride
Mean Corpuscular Volume	Bilirubin
Mean Corpuscular Haemoglobin	Alkaline Phosphatase
Platelet	Aspartate Aminotransferase
Leukocytes	Alanine Aminotransferase
Absolute Neutrophils	Lactate Dehydrogenase
Absolute Lymphocytes	Gamma Glutamyl Transferase
Absolute Neutrophils	Protein
Absolute Eosinophils	Albumin
Absolute Basophils	Calcium
	Magnesium
	Phosphate
	Urea
	Urate
	Creatinine
	Glucose

5.4.3 Dispensing

5.4.3.1 Receipt and storage of the Investigational Medicinal Product

The ATIMP vector will be dispensed on the same day as administration according to study specific working instructions, with a 1-hour window for administration after ATIMP has thawed at room temperature.

5.4.4 Dosage and dosage modifications

Trial participants will receive 1 of 3 different doses of ATIMP within the range proven to be safe in the preclinical animal studies.

1) low dose

2) intermediate dose

3) high dose

The ATIMP will be diluted as appropriate for the specific dose intended immediately prior to intraocular administration in Hartmann's solution at the time of administration. The CI/PI will prepare the appropriate dilution, and this will be checked in the operating theatre by a second individual prior to administration. The check will be recorded in the patient's source data notes.

Further details for dose-escalation criteria are included in Sections 4.3.2.

5.4.5 Accountability

The ATIMP will be prescribed and handled according to the ATIMP management plan applicable for the site.

For accurate accountability, the following information will be recorded when the ATIMP is administered:

- i. date
- ii. participant identification
- iii. batch number
- iv. volume and dose of ATIMP administered
- v. name of CI/PI administering ATIMP
- vi. ATIMP name/code
- vii. Trial reference code
- viii. Expiry date

Surplus ATIMP will be destroyed according to existing SOPs, using methods suitable for destruction of genetically modified organisms.

A system will be set-up to ensure the traceability of the ATIMP from the starting material, through to administration to the participant and destruction. A comprehensive ATIMP management plan and associated forms will be in place to ensure that the required accountability and traceability data is retained.

5.4.6 Compliance and Adherence

Full compliance is expected since the ATIMP will be surgically delivered by the CI or a delegated vitreoretinal surgeon. The aim is to target the administered volume into the subretinal space. Any deviation from this will be noted in the CRF. See section 5.4.8 (Overdose of trial medication) about the assessment of adherence to the protocol defined delivery of the product.

5.4.7 Concomitant Care

Concomitant use of other medications should be avoided unless clinically necessary, should be used with caution, and appropriately documented on study logs where used. All concomitant medications (including steroids) must be recorded in the CRF from the day of informed consent.

5.4.8 Overdose of Trial Medication

A single intraocular administration of ATIMP will be performed by the operating surgeon (CI or a delegated vitreo-retinal surgeon). The volume of vector delivered to the target site will be measured by the syringe plunger scale and recorded in the CRF.

Any overdose will be reported to the sponsor. This is a Phase I/II exploratory study and the possible impact of any overdose will be considered in the final analysis. Given that this is a single administration study, the trial participant will not be withdrawn but the collected data will be analysed separately in comparison with the data from the participant's baseline assessments and from other treated participants. Any concern about accurate dosing may warrant suspension of the trial pending appropriate investigation.

Overdose of ATIMP may result in development of Adverse Events of various severities that will be recorded and reported as outlined in Section 5.11.3.

5.4.9 Protocol Treatment Discontinuation

5.4.9.1 Participant withdrawal

In consenting to the trial, participants are consenting to ATIMP administration, trial follow-up and data collection.

As participation in the trial is entirely voluntary, the participant may choose to discontinue trial participation at any time without penalty or loss of benefits to which they would otherwise be entitled.

Although not obliged to give a reason for discontinuing their participation, a reasonable effort should be made to establish this, whilst remaining fully respectful of the participant's rights.

Should a participant withdraw from the study, a withdrawal CRF documenting the reason for withdrawal will be completed, in addition to the procedures and CRF for the final visit (12 month) assessments, with the participant's consent. However, participants will be encouraged to participate in any of the planned schedule for the trial whilst arranging a visit for routine (annual) clinical follow-up.

Participants who withdraw prior to vector administration will be regarded as off-protocol and their primary ophthalmologist will resume normal standard of care. Any participant who withdraws prior to administration of ATIMP may be replaced in the study. Participants who withdraw from the study after vector administration will be encouraged to have follow-up safety and efficacy investigations with their consent, so that the consequences of vector administration can be documented, and the data analysed. The CMT may choose to replace a participant who withdraws after vector administration.

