5.3.1.6.4 Enrolment (Randomisation)

Participants who fulfil the study entry criteria based on the results of all screening assessments will be enrolled (randomised) in the trial. ATIMP will be administered within 3 months of enrolment for participants randomised to immediate treatment. If the ATIMP is not delivered within 3 months of enrolment, all screening tests with the exception of genetic testing, visual mobility and electrophysiological assessment will be repeated and eligibility for enrolment re-assessed³. For participants randomised to the control (deferred treatment) arm, study assessments will be performed per the Table 4: Trial Assessments (Deferred treatment arm).

Participants who withdraw or are withdrawn from the study for any reason prior to ATIMP administration may be substituted in the study.

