5.6.1 Early Stopping of Follow-up

If a participant chooses to discontinue their trial treatment, they should continue to be followed up as closely as possible to the follow-up schedule defined in the protocol, providing they are willing. If, however, the participant exercises the view that they no longer wish to be followed up either, this view must be respected. Data already collected will be kept and included in analyses according to the intention-to-treat principle for all participants who stop follow up early.

Participants who stop trial follow-up early may be replaced.

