1.2. Trial Design

This is an open-label, phase I/II dose-escalation trial to determine the safety and efficacy of subretinal administration of the study agent (AAV5-hRKp.RPGR) in subjects with genetically confirmed RPGR-XLRP. As shown in Schema of treatment groups with study phases in Figure 1 and Schema of treatment groups within study phases in Figure 2, MGT-RPGR-009 includes three phases, dose escalation phase in adult RPGR patients, dose confirmation phase in pediatric RPGR patients, and randomized expansion phase in adult RPGR patients.

Figure 1: MGT009 Study Design Schematic

[figure not shown]
[figure not shown]

Figure 2: Schema of treatment groups within study phases

In the dose escalation phase, subjects were administered a single dose of ATIMP in cohorts of 3-4 subjects at a time. Based on a review of safety data, the Independent Data Monitoring Committee (IDMC) made recommendations on whether the dose was to be escalated or whether additional subjects were needed to repeat a dose in the cohort. The IDMC concurred on dosing a pediatric cohort at the intermediate dose prior to moving into the expansion cohort.

After an acceptable safety profile had been established in adults, the IDMC agreed to the sponsor's plan for administering the intermediate and low doses in the expansion phase. In the expansion phase, subjects were randomized to either immediate treatment with the low dose, or immediate treatment with the intermediate dose, or to a 6-month deferred-treatment group to receive either the low dose or the intermediate dose. Subjects in the immediate treatment arm were followed for 12 months before migrating to the long-term extension study, MGT-RPGR-010. Subjects in the deferred treatment arm were followed for at least 6 months before crossing them over to active treatment; at the 12-month time point these subjects also migrated to the long-term follow up study, MGT-RPGR-010. 6-month data from deferred arm during deferred period prior to treatment serves as the concurrent control group.

Adults were defined as subjects aged 16+ in the United Kingdom and aged 18+ in the United States.

Safety and efficacy are assessed for 12 months following the intervention by clinical examination and special investigations according to the schedule in Section 5.6 of the protocol.

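### The protocol's rules on follow-up after withdrawal before vector conflict, and within the comparison window the off-protocol rule falls only on the deferred control arm

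*Protocol*

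**What the plan says.** Protocol 5.4.9.1 contains three statements about a participant who withdraws.

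- A general paragraph, with no limit on timing, asks for a withdrawal form "in addition to the procedures and CRF for the final visit (12 month) assessments, with the participant's consent", and adds that "participants will be encouraged to participate in any of the planned schedule for the trial".
- A sentence for withdrawal before vector: "Participants who withdraw prior to vector administration will be regarded as off-protocol and their primary ophthalmologist will resume normal standard of care". Such a participant may be replaced. Section 5.3.1.6.4 agrees that those who leave "prior to ATIMP administration may be substituted in the study".
- A sentence for withdrawal after vector: "Participants who withdraw from the study after vector administration will be encouraged to have follow-up safety and efficacy investigations with their consent". The reason given is that the effects of the vector can then be documented.

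Protocol 5.10.2 also confines its encouragement to people who withdraw after the intervention. Protocol 5.6.1 sets no such limit: "If a participant chooses to discontinue their trial treatment, they should continue to be followed up as closely as possible to the follow-up schedule", if willing, and data already collected are analysed by intention to treat.

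On the control group, SAP 1.2 says: "6-month data from deferred arm during deferred period prior to treatment serves as the concurrent control group". Protocol Table 4 places the deferred arm's Month 3 and Month 6 assessments before ATIMP.

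**The concern.** Splitting the follow-up rule at vector administration suits a study in which everyone is dosed. The protocol's amendment log records that the randomised component was added at v9.0, and the withdrawal text makes no provision for an untreated control period.

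The primary efficacy comparison needs perimetry at both Week 13 and Week 26 in both arms. If sites pursue visits from dosed immediate participants who withdraw but release deferred participants who do so, missing data will differ by arm because of how the protocol was read. The trial is open label for participants, so a deferred participant knows he is untreated, and a decision to leave could be related to how he thinks his vision is changing. Missing control data could then be informative in a group of at most 16.

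**Working it through.** **1. The rules side by side**

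| Protocol section | Who is covered | What is sought |
|---|---|---|
| 5.4.9.1, general paragraph | Any withdrawal, any time | Final-visit assessments with consent; encouragement to attend planned visits |
| 5.4.9.1, off-protocol sentence | Withdrawal before vector | Return to usual care; may be replaced |
| 5.4.9.1, following text | Withdrawal after vector | Encouragement to have safety and efficacy follow-up |
| 5.6.1 | Anyone giving up trial treatment | Stay on schedule if willing |
| 5.10.2 | Withdrawal after the intervention | Encouragement to attend planned follow-up |

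For withdrawal before vector, the first and fourth rows point towards continued visits. The second points away from them, and the fifth is silent.

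**2. Where each rule falls in the comparison window**

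SAP 2.5 sets Study Day 1 for the immediate arms as the day of ATIMP. Every immediate-arm withdrawal from Day 1 to Week 26 is therefore after vector. For the deferred period, Day 1 is the end of the last baseline visit, and ATIMP follows the Month 6 assessments. Every control withdrawal before the Week 26 control visit is therefore before vector. Within the window, the off-protocol sentence applies only to controls and the after-vector encouragement only to dosed immediate participants.

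Outside the window this is not so. Protocol 5.3.1.6.4 allows up to 3 months between enrolment and surgery in the immediate arms, and withdrawals in that interval are off-protocol too.

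**3. What the SAP does with a missing visit**

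Under SAP 5.3.1 and 5.3.3, a participant missing Week 13 or Week 26 leaves both numerator and denominator. A single final-visit assessment at withdrawal would usually not supply both. SAP 5.3.2 names a treatment policy strategy but lists no intercurrent event, so declining the deferred surgery is not addressed.

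**4. Size**

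The plan gives no power, response rate or dropout rate to reproduce (Protocol 5.7 has no formal sample size calculation). From Protocol 5.9.1, 48/3 = 16 per arm, giving 2 × 16 = 32 immediate and 16 deferred at most.

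- Share of controls lost: 1/16 = 6.25%; 2/16 = 12.5%.
- Standard error of the difference with k controls missing, relative to none missing, assuming equal variances: √[(1/32 + 1/(16−k)) / (1/32 + 1/16)]. This is 1.022, 1.047, 1.074 and 1.106 for k = 1 to 4.
- Range for the control response rate with x observed responders: x/16 to (x+k)/16. With x = 0 this is 0% to 12.5% for k = 2, and 0% to 25% for k = 4.

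The next table uses assumed counts and an unstratified two-sided Fisher's exact test; the SAP's test is stratified by age. No observed control responds, and the last column supposes that every missing control would have responded.

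| Immediate responders | Controls missing | p, observed only | p, missing all respond |
|---|---|---|---|
| 12/32 | 1 | 0.005 (0/15) | 0.036 (1/16) |
| 12/32 | 2 | 0.009 (0/14) | 0.098 (2/16) |
| 14/32 | 2 | 0.004 (0/14) | 0.0501 (2/16) |
| 16/32 | 2 | 0.001 (0/14) | 0.013 (2/16) |

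The loss of precision is small. The larger exposure is to informative missingness: at intermediate effects, two controls could decide the primary test, through which all alpha passes (SAP 5.5). These are worst-case bounds and do not predict what will happen.

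**The case against.** A reader might infer that the protocol forbids following anyone who withdraws before vector, so that control data are lost by rule and in one arm only. The documents do not support that.

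- No section bars collection. The general paragraph of 5.4.9.1 and section 5.6.1 both favour continued attendance, and neither is limited to dosed participants.
- The off-protocol rule is not worded by arm. It also covers immediate participants awaiting surgery, and SAP 2.3.2 excludes undosed immediate participants from the full analysis set.
- Replacement is not confined to controls. Section 5.4.9.1 also allows replacement after vector, and 5.6.1 allows it for anyone who stops follow-up. Nothing says that a replacement takes the vacated arm; 5.9.1 describes allocation by randomisation.

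It can also be argued that 5.6.1 concerns giving up treatment while 5.4.9.1 concerns leaving the study, so that the two do not clash. That reading is possible, and on it a deferred participant who merely declines surgery would stay on schedule. But no section draws that line for the deferred arm, and a site could reasonably let the specific off-protocol sentence override the general one.

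Finally, the primary objective is safety, the SAP describes the efficacy comparison as preliminary, the protocol expects high retention, and no withdrawal rate is given. These points lower the severity. They leave the conflict unresolved.

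**Conclusion.** The point stands as a conflict between stated rules that permits differential follow-up in the randomised phase. It does not show that control data were or will be lost. The asymmetry between arms is real, but only within the Day 1 to Week 26 window. Each control affected is 6.25% of an arm of at most 16. The effect on the result depends on how many withdraw, how sites read the text and whether leaving is related to vision, none of which the documents state.

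This is a worthwhile correction, short of one on which the plan's acceptability depends. The SAP is based on protocol v12.0, while the amendment log in the supplied protocol ends at v11.0, so the v12.0 wording could not be checked.

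**What to change.** Reconcile Protocol 5.4.9.1, 5.6.1 and 5.10.2. For the randomised phase, state that a deferred participant who declines ATIMP, or withdraws before it, is asked, with consent, to attend the Month 3 and Month 6 assessments already in Table 4, and is analysed in the deferred arm. State in 5.4.9.1 and 5.3.1.6.4 that any replacement is newly randomised and does not inherit the vacated arm.

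Do not extend the Table 4 schedule to undosed immediate participants by protocol wording alone. They have no Study Day 1 under SAP 2.5 and are outside the full analysis set under SAP 2.3.2, so both sections would have to change as well.

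The cost is protocol wording and some site effort to retain people who will not be treated; no new visits are needed for the deferred arm. The SAP describes expansion-phase randomisation in the past tense. For visits already past, what remains is to report withdrawals by arm and by timing relative to vector, and whether later visits were sought.

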5.4.9.2 Trial Stopping Rules

The CI and Sponsor retain the right to terminate the study. Specific circumstances that may precipitate such termination are as follows:

- Unanticipated adverse medical experience in this or other studies indicating a potential health hazard caused by the ATIMP
- 2. Significant protocol deviation and lack of compliance and cooperation on the part of an investigator, which endangers the safety of the participants or the validity of the trial
- Death of a participant at any time point after ATIMP administration that is possibly, probably, or definitely related to the ATIMP
- 4. The occurrence of a non-ocular malignancy at any point after gene transfer that is possibly, probably, or definitely related to the ATIMP

5.5 Outcomes

5.5.1 Primary Outcomes

The primary safety outcome is defined as absence of any of the below occurring during the 9 weeks following administration, at least possibly related to the ATIMP, not surgery alone:

Reduction in visual acuity by 15 ETDRS letters or more

- Severe unresponsive inflammation
- Infective endophthalmitis
- Ocular malignancy
- Grade III or above non-ocular SUSAR (see section 5.11.3)

5.5.2 Secondary Outcomes

The secondary outcomes are measures of the efficacy of the ATIMP; these will be performed on an individual participant basis and will be descriptive in nature.

- Slowing or halting of progressive deterioration in retinal structure or visual function that is greater
 than the baseline variation for that test and is sustained for at least 2 consecutive assessments.
 Slowing or halting of progression over time may be facilitated by comparing identical structural
 and functional assessments acquired prior to intervention/injection to better determine rate of
 change over time in this slowly progressive disease.
 - Historical images will be collected wherever possible with written informed consent from the participants
- Any improvements in visual function from baseline that are greater than the baseline variation and are sustained for at least two consecutive assessments.
- Any improvement in retinal function from pre-intervention that is greater than baseline variation and measurable by electrophysiology (pattern ERG, multifocal ERG or full-field ERG).
- Health- and Vision-Related Quality of life (HRQoL, VRQOL) will be assessed by the Impact of Visual Impairment (IVI) questionnaire, the Low Luminance Questionnaire (LLQ), the EQ5D HRQoL questionnaire (EQ-5D-5L or EQ-5D-Y), changes in disease severity and health status will be assessed by the Patient Global Impression of Severity (PGIS), the Patient Global Impression of Change (PGIC) and the Clinician Global Impression of Change (CGIC) measures.

¹Baseline assessments may be performed on the same day where considered logistically and clinically appropriate. All assessments should be performed as soon as possible; however, all baseline assessments must be done within a 3 month period.

²Additional baseline assessments are permitted if there is inconsistency between the screening and first baseline assessment

³Measurements for vital signs include: blood pressure, pulse, respiration rate, arterial oxygen saturation, temperature, height and weight

⁴Visual acuity at day 1 and 3 will be assessed using the previous refraction.

⁵ERG assessments may be performed under general anaesthesia if considered appropriate

⁶ HBV testing is only mandatory for participants if required by local practice. Participants with chronic hepatitis B virus infection as indicated by detectable surface antigen will be excluded from the study. For those with negative surface antigen, but positive hepatitis B core antibody, testing will be performed to confirm Hepatitis B viral load following completion of steroid treatment.

⁷ Additional monitoring of liver enzymes will be performed following steroid treatment

⁸ Patients who screened failed under a previous version of the protocol may be reconsidered for eligibility and will not be required to repeat tests provided these were performed within the visit window from the original screening date.

⁹ Two Treatment Experience interviews will be administered to the low and intermediate dose active treatment group at 6 months (Visit 14) and at 12 months post-treatment (either at the visit or within 14 days of the final study visit - visit 16), or upon early withdrawal.

*Per section 5.4.2.1 assessments listed as "performed in all participants" must be performed, every effort must be made to perform all other assessments where possible

Table 4: Trial Assessments (Deferred Treatment arm) *

, unic ii		nts (Deferred				uring	ř –			 	· · · ·	ř	· · · · ·				_
	Up to 4 months prior to randomisation	Randomisation	Ва	Baseline ^{1, 2}		M3 ⁸	M6 ⁸	ATIMP admin after M6 assessments	D1 post- ATIMP admin	D3 post- ATIMP admin	W1 post- ATIMP admin	W2 post- ATIMP admin	W4 post- ATIMP admin	W6 post- ATIMP admin	W9 post- ATIMP admin	M3 post ATIMP admin	M6 post ATIMP admin
Flexibility of schedule (+ days)			8			± 14D	14D	+14D	+ 0D	+ 1D	+ 2D	+ 4D	+ 7D	+ 7D	± 7D	± 14D	± 14D
Visit number	1		2	3	4	5	6	7	8	9	10	11	12	13	14	15	16
Informed consent	•																
Physical exam	•																es.
Medical history	•					•				7	•		•	•		•	•
Eligibility determination	•						•										
IMP administration								*			70	(ç					
Adverse event review			•	•	•	•	•		S A	•		•	•	•	•	S	
Concomitant medication review	v.		•	● R	•	•	•		•8	•	•	•	•	•	3. T	• 3	
Genetic screening	•	9									10	20			3		3
Vital signs (including height and weight) ³	•		•				•		•8		•	•	•	•			
Randomisation		*										9.					ō.
Haematology			•						•33		•13		•	(• X			
Biochemistry/ glucose			•)•				•.1	•	•	•	•7		
Hepatitis B (HBV) testing ⁶	•																
Serology		,	•			8						10 01	•			•	•
PCR													•				

	Up to 4 months prior to randomisation	Randomisation	Ba	Baseline ^{1, 2}		M3 ⁸	M6 ⁸	ATIMP admin after M6 assessments	D1 post- ATIMP admin	D3 post- ATIMP admin	W1 post- ATIMP admin	W2 post- ATIMP admin	W4 post- ATIMP admin	W6 post- ATIMP admin	W9 post- ATIMP admin	M3 post ATIMP admin	M6 post ATIMP admin
Flexibility of schedule (+ days)						± 14D	14D	+14D	+ 0D	+ 1D	+ 2D	+ 4D	+ 7D	+ 7D	± 7D	± 14D	± 14D
QoL questionnaires (IVI, EQ5D-5L, EQ5D- Y, Low Luminance Questionnaire), Patient Global Impression of Severity			•				•									•	•
Patient Global Impression of Change and Clinician Impression of Change												9					•
Treatment Experience Interview ¹⁰																	•
Visual acuity ⁴			•	•	•	•	•		•8		•)	•	•	(•)(•	
Low Luminance Visual Acuity			•	•	•											•	•
Contrast sensitivity			•	•	•	•	•			ra s	75	£6			24	•8	
Reading speed Colour vision assessments		2	•	•	•	•	•	3					S 5-			•	•
Static visual fields			•	•	•	•	•					65	· V.			•	
Microperimetry			•	•	•	•	•					i i				•	•
Ocular examination			•	•	•	•	•		•	•	•	•	•	•	•	•	•
Fundus photography			•			•	•		•	***	•		•	•	**•		•

	Up to 4 months prior to randomisation	Randomisation	Ba	Baseline ^{1, 2}		M3 ⁸	M6 ⁸	ATIMP admin after M6 assessments	D1 post- ATIMP admin	D3 post- ATIMP admin	W1 post- ATIMP admin	W2 post- ATIMP admin	W4 post- ATIMP admin	W6 post- ATIMP admin	W9 post- ATIMP admin	M3 post ATIMP admin	M6 post ATIMP admin
Flexibility of schedule (+ days)						± 14D	14D	+14D	+ 0D	+ 1D	+ 2D	+ 4D	+ 7D	+ 7D	± 7D	± 14D	± 14D
Optical coherence tomography	•		•	•	•	•	•		100 S	•	•		•				
Adaptive optics imaging			•				•										•
Fundus autofluorescence			•	•	•	•	•			2						•	
Full field electroretinography ⁵			•			•											•
Pattern electroretinography ⁵			•			•											•
Multifocal electroretinography ⁵			•			•											
Visual mobility assessment ^{8 9}	•					ě	•								ii	•	•

¹Baseline assessments may be performed on the same day where considered logistically and clinically appropriate. All assessments should be performed as soon as possible however all baseline assessments must be done within a 4 month period.

²Additional baseline assessments are permitted if there is inconsistency between the screening and first baseline assessment

³Measurements for vital signs include: blood pressure, pulse, respiration rate, arterial oxygen saturation, temperature, height and weight

⁴ Visual acuity at day 1 and 3 post-ATIMP administration will be assessed using the previous refraction.

⁵ERG assessments may be performed under general anaesthesia if considered appropriate

⁶ HBV testing is only mandatory for participants if required by local practice. Participants with chronic hepatitis B virus infection as indicated by detectable surface antigen will be excluded from the study. For those with negative surface antigen, but positive hepatitis B core antibody, testing will be performed to confirm Hepatitis B viral load following completion of steroid treatment.

*Per section 5.4.2.1 assessments listed as "performed in all participants" must be performed, every effort must be made to perform all other assessments where possible

⁷ Additional monitoring of liver enzymes will be performed following steroid treatment

⁸ Month 3 and 6 assessments should be planned for +3 months and +6 months after the last baseline assessment (Baseline visit 4)

⁹ Patients who screened failed under a previous version of the protocol may be reconsidered for eligibility and will not be required to repeat tests provided these were performed within the visit window from the original screening date.

¹⁰ Treatment Experience interviews will be administered to all subjects either at or within 14 days of the final study visit (month 6 / visit 16), or upon early withdrawal.

